13.2 Subject site transfers

This document cannot be used to support any marketing au
RED

nd any extensions or variations thereof.

13.3 PCST criteria

13.3.1 Hematology parameters

Parameter	UCB Conventional Units	SI Units	CF
Hematocrit	For 1 m to < 6 m: ≤ 25% For 6 m to < 2 y: ≤ 27% For 2 y to < 4 y: ≤ 29% For 4 y to < 12 y: ≤ 32% (Female[F]); ≤ 35% (Male [M]) For ≥ 12 y: ≤ 32% (F); ≤ 37% (M)	For 1 m to < 6 m: ≤ 0.25 For 6 m to < 2 y: ≤ 0.27 For 2 y to < 4 y: ≤ 0.29 For 4 y to < 12 y: ≤ 0.32 (F); ≤ 0.35 (M) For ≥ 12 y: ≤ 0.32 (F); ≤ 0.37 (M)	0.01
Hemoglobin	For < 6 m: ≤ 9.7 g/dL For 6 m to < 12 y: ≤ 10.0 g/dL For ≥ 12 y: ≤ 9.5 g/dL (F); ≤ 11.5 g/dL (M)	For < 6 m: ≤ 97 g/L For 6 m to < 12 y: ≤ 100 g/L For ≥ 12 y: ≤ 95 g/L (F); ≤ 115 g/L (M)	10
Platelets	≤ 75 x 10 ⁹ /L or ≥ 700 x 10 ⁹ /L	≤ 75 x 10 ⁹ /L or ≥ 700 x 10 ⁹ /L	Not applicable (N/A)
White Blood Cell (WBC)	For < 17 y: ≤ 3.0 x 10 ⁹ /L or ≥ 20 x 10 ⁹ /L; For ≥ 17 y: ≤ 2.8 x 10 ⁹ /L or ≥ 16 x 10 ⁹ /L;	For < 17 y: ≤ 3.0 x 10 ⁹ /L or ≥ 20 x 10 ⁹ /L; For ≥ 17 y: ≤ 2.8 x 10 ⁹ /L or ≥ 16 x 10 ⁹ /L;	N/A
Red Blood Cell (RBC)	For < 17 y: ≤ 2.5 x 10 ⁶ /mm ³ For ≥ 17 y: ≤ 2.0 x 10 ⁶ /mm ³ (F); ≤ 2.5 x 10 ⁶ /mm ³ (M)	For < 17 y: ≤ 2.5 x 10 ¹² /L For ≥ 17 y: ≤ 2.0 x 10 ¹² /L (F); ≤ 2.5 x 10 ¹² /L (M)	1
Eosinophils	≥ 10% or ≥ 0.7 x 10 ⁹ /L	≥ 0.10 or ≥ 0.7 x 10 ⁹ /L	0.01 or N/A
Neutrophils	≤ 15% or ≤ 1.0 x 10 ⁹ /L	≤ 0.15 or ≤ 1.0 x 10 ⁹ /L	0.01 or N/A
Basophils	≥ 5% or ≥ 0.4 x 10 ⁹ /L	≥ 0.05 or ≥ 0.4 x 10 ⁹ /L	0.01 or N/A
Monocytes	≥ 20% or ≥ 1.5 x 10 ⁹ /L	≥ 0.20 or ≥ 1.5 x 10 ⁹ /L	0.01 or N/A
Lymphocytes	For 1 m to < 6 m: ≤ 22% or ≥ 80% ≤ 2.1 x 10 ⁹ /L or ≥ 8.5 x 10 ⁹ /L For 6 m to < 2 y: ≤ 15% or ≥ 80% ≤ 1.5 x 10 ⁹ /L or ≥ 7.5 x 10 ⁹ /L For 2 y to < 12 y: ≤ 12% or ≥ 80% ≤ 1.0 x 10 ⁹ /L or ≥ 7.5 x 10 ⁹ /L For 12 y to < 17 y: ≤ 10% or ≥ 80% ≤ 0.5 x 10 ⁹ /L or ≥ 5.5 x 10 ⁹ /L For ≥ 17 y: ≤ 10% or ≥ 80% ≤ 0.5 x 10 ⁹ /L or ≥ 4.5 x 10 ⁹ /L	For 1 m to < 6 m: ≤ 0.22 or ≥ 0.80 ≤ 2.1 x 10 ⁹ /L or ≥ 8.5 x 10 ⁹ /L For 6 m to < 2 y: ≤ 0.15 or ≥ 0.80 ≤ 1.5 x 10 ⁹ /L or ≥ 7.5 x 10 ⁹ /L For 2 y to < 12 y: ≤ 0.12 or ≥ 0.80 ≤ 1.0 x 10 ⁹ /L or ≥ 7.5 x 10 ⁹ /L For 12 y to < 17 y: ≤ 0.10 or ≥ 0.80 ≤ 0.5 x 10 ⁹ /L or ≥ 5.5 x 10 ⁹ /L For ≥ 17 y: ≤ 0.10 or ≥ 0.80 ≤ 0.5 x 10 ⁹ /L or ≥ 4.5 x 10 ⁹ /L	0.01 N/A 0.01 N/A 0.01 N/A 0.01 N/A 0.01 N/A

13.3.2 Blood chemistry parameters

Parameter	UCB Conventional Units	SI Units	CF
AST (SGOT)	≥ 3 times of ULN	≥ 3 times of ULN	N/A
ALT (SGPT)	≥ 3 times of ULN	≥ 3 times of ULN	N/A
ALP	For < 17 y: ≥ 2 times of ULN, if normal range adjusted to the age range; For ≥ 17 y: ≥ 3 times of ULN	For < 17 y: ≥ 2 times of ULN, if normal range adjusted to the age range; For ≥ 17 y: ≥ 3 times of ULN	N/A
GGT	≥ 3 times of ULN, if baseline value ≤ 3 times of ULN	≥ 3 times of ULN, if baseline value ≤ 3 times of ULN	N/A
BUN	≥ 30 mg/dL	≥ 10.71 mmol/L	0.357
Urea	≥ 60 mg/dL	≥ 10.02 mmol/L	0.167
Creatinine	For < 17 y: ≥ 1.5 mg/dL; For ≥ 17 y: ≥ 2.0 mg/dL	For < 17 y: ≥ 132.6 umol/L; For ≥ 17 y: ≥ 176.8 umol/L	88.4
Creatinine clearance (calc)	For < 12 y: < 70 ml/min (Schwartz) ^(a) For ≥ 12 y: < 70 ml/min (Cockcroft) ^(b)	For < 12 y: < 70 ml/min (Schwartz) ^(a) For ≥ 12 y: < 70 ml/min (Cockcroft) ^(b)	N/A
Total bilirubin	≥ 2.0 mg/dL	≥ 34.2 umol/L	17.1
Glucose	≤ 50 mg/dL or ≥ 180 mg/dL	≤ 2.775 mmol/L or ≥ 9.99 mmol/L	0.0555
Total Protein	For ≥ 1 m to < 6 m: ≤ 3.6 g/dL or ≥ 7.8 g/dL For ≥ 6 m to < 17 y: ≤ 4.7 g/dL or ≥ 9.5 g/dL For ≥ 17 y: ≤ 4.5 g/dL or ≥ 9.0 g/dL	For ≥ 1 m to < 6 m: ≤ 36 g/L or ≥ 78 g/L For ≥ 6 m to < 17 y: ≤ 47 g/L or ≥ 95 g/L For ≥ 17 y: ≤ 45 g/L or ≥ 90 g/L	10
Albumin	For < 17 y: ≤ 2.4 g/dL or ≥ 6.5 g/dL For ≥ 17 y: ≤ 2.5 g/dL or ≥ 6.5 g/dL	For < 17 y: ≤ 24 g/L or ≥ 65 g/L For ≥ 17 y: ≤ 25 g/L or ≥ 65 g/L	10
Globulin	For < 17 y: ≤ 1.2 g/dL or ≥ 5.0 g/dL For ≥ 17 y: ≤ 1.5 g/dL or ≥ 5.0 g/dL	For < 17 y: ≤ 12 g/L or ≥ 50 g/L For ≥ 17 y: ≤ 15 g/L or ≥ 50 g/L	10
Sodium	For < 17 y: ≤ 120 mEq/L or ≥ 155 mEq/L For ≥ 17 y: ≤ 115 mEq/L or ≥ 155 mEq/L	For < 17 y: ≤ 120 mmol/L or ≥ 155 mmol/L For ≥ 17 y: ≤ 115 mmol/L or ≥ 155 mmol/L	1
Potassium	For < 17 y: ≤ 3.0 mEq/L or ≥ 6.5 mEq/L For ≥ 17 y: ≤ 3.0 mEq/L or ≥ 5.8 mEq/L	For < 17 y: ≤ 3.0 mmol/L or ≥ 6.5 mmol/L For ≥ 17 y: ≤ 3.0 mmol/L or ≥ 5.8 mmol/L	1
Calcium	For < 17 y: ≤ 7 mg/dL or ≥ 11.5 mg/dL For ≥ 17 y: ≤ 7 mg/dL or ≥ 15.5 mg/dL	For < 17 y: ≤ 1.75 mmol/L or ≥ 2.875 mmol/L For ≥ 17 y: ≤ 1.75 mmol/L or ≥ 3.875 mmol/L	0.25

Uric Acid	For < 12 y: ≥ 8 mg/dL For ≥ 12 y: ≥ 8 mg/dL (F); ≥ 9.5 mg/dL (M)	For < 12 y: ≥ 475.84 umol/L For ≥ 12 y: ≥ 475.84 umol/L (F); ≥ 565.06 umol/L (M)	59.48
Cholesterol	≥ 300 mg/dL	≥ 7.77 mmol/L	0.0259
HDL	≤ 25 mg/dL	≤ 0.65 mmol/L	0.0259
LDL	≥ 200 mg/dL	≥ 5.18 mmol/L	0.0259
Triglycerides	≥ 300 mg/dL	≥ 3.42 mmol/L	0.0114

(a) Schwartz equation (patients <12): $Cr\ Cl\ ml/min = [Height\ (cm) * 0.55] / \text{serum creatinine}$
 
(b) Cockcroft equation (patients ≥12): Male: $Cr\ Cl\ ml/min = [(140-age) \times body\ weight\ (kg)] / (72 \times \text{serum creatinine})$, Female: $Cr\ Cl\ ml/min = [(140-age) \times body\ weight\ (kg)] / (72 \times \text{serum creatinine}) \times 0.85$
 
ALT=alanine aminotransferase; ALP=Alkaline phosphatase; AST=aspartate aminotransferase; BUN=blood urea nitrogen; CR CL=creatinine clearance; GGT=Gamma-glutamyl transpeptidase; HDL=High-density lipoprotein; LDL=low-density lipoprotein; SGOT=serum glutamic oxaloacetic transaminase; SGPT=serum glutamic pyruvic transaminase; ULN=Upper Limit of Normal.
			

This document cannot be used to support any marketing authorization applications and any extensions or variations thereof.

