10.2.16 Laboratory Assessments

At the following visits: Full Evaluation Visit, Yearly Evaluation Visit, Early Discontinuation Visit, and Final Visit, laboratory assessments will be conducted using standard methods at a central laboratory. At the Entry Visit, data will be transferred electronically from the last Evaluation Visit of the previous study and should not be recorded on the CRF. The central laboratory will provide the Investigator with dedicated, standardized sampling equipment (labels, needles, tubes), and a study-specific laboratory manual, which will explain how to use the equipment and how to ship the samples back to the central laboratory. Results for hematology, chemistry, urinalysis and serum pregnancy tests (if the local urine pregnancy test was positive) will be provided by fax to the Investigator within 72 hours after sample receipt.

Total blood volume drawn for clinical laboratory assessments will be maximum 11 mL/sampling. Subject should preferably be fasting. Study medication intake must not be delayed.

The following laboratory assessments will be conducted:

- Blood chemistry: glucose, urea, creatinine, sodium, potassium, calcium, phosphorus (inorganic), total protein, albumin, total bilirubin, alkaline phosphatase, aspartate aminotransferase/serum glutamic oxaloacetic transaminase (ASAT/SGOT), alanine aminotransferase/serum glutamic pyruvic transaminase (ALAT/SGPT), gamma-glutamyltranspeptidase (GGT), and uric acid.
- The creatinine clearance (Cr Cl) will be calculated by the Cockcroft's formula (only at Entry Visit):
 - male: $Cr\ Cl\ mL/min = [(140 - age) \times body\ weight] / (72 \times serum\ creatinine\ (mg/dl))$,
 - female: $Cr\ Cl\ mL/min = [(140 - age) \times body\ weight] / (72 \times serum\ creatinine\ (mg/dl)) \times 0.85$.
- Hematology: white blood cells (WBC), red blood cells (RBC), hemoglobin, hematocrit, mean corpuscular volume (MCV), mean corpuscular hemoglobin (MCH), mean corpuscular hemoglobin concentration (MCHC), platelet count, lymphocytes

This document is a draft of a supporting document for the application and is not for publication and may be subject to variations thereof.

(number, %), monocytes (number, %), neutrophils (number, %), eosinophils (number, %), basophils (number, %), other cells (number, %).

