3.3 Definition of Baseline Values

Baseline for all study outcomes will be based on baseline from the previous studies. For assessments performed at scheduled and unscheduled visits, Baseline will generally be the last result obtained or prior to the randomization visit of the previous study. Baseline will be defined separately for each hematology, blood chemistry, and urinalysis parameter.

Baseline for the evaluation of seizure frequency and seizure days will be calculated from the core study seizure diary based on the rules defined in Section 3.8.1 .

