11.3.1 Hematology and blood chemistry parameters

Observed values for each planned hematology and blood chemistry parameter will be summarized for Baseline, Study Entry, and each scheduled visit during the Evaluation Period for which laboratory parameters were assessed, Last Value, EDV, and FV. Change from Baseline will be summarized for all post-Baseline time points including EV. Only laboratory parameters planned per protocol will be summarized; results for laboratory parameters not planned per the protocol will only be provided in subject data listings.

The number and percentage of subjects with an on-treatment potentially clinically significant treatment-emergent (PCST) value, PCST low value, and PCST high value will be summarized. This summary will consider all assessments after the first dose of BRV and prior to or on the date of the last dose of BRV.

Additionally, the number and percentage of subjects with a PCST value, PCST low value, and PCST high value will be summarized for Baseline, Study Entry, each visit during the Evaluation Period for which laboratory parameters were scheduled to be assessed, EDV, Last Value, and FV. Percentages for each parameter and time point will be relative to the number of subjects with a value at that time point.

PCST criteria (Sections 13.3.1 and 13.3.2) are based on FDA Division of Neuropharmacologic Drug Products guidelines with some UCB-defined additions.

Creatinine clearance, when available from the central laboratory, will be provided in subject data listings only and will not be summarized.

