11.4.1 Vital signs

Vital signs are assessed at all FEVs, MEVs, YEVs, EDVs, and at FV, and may also be assessed at Unscheduled Visits. Body weight is assessed at all FEVs, YEVs, EDVs, and at FV, and may also be assessed at Unscheduled Visits.

Observed values for SBP, DBP, pulse rate, and body weight will be summarized for Baseline, Study Entry, each visit during the Evaluation Period for which vital signs or body weight were assessed, EDV, Last Value, and FV. Changes from Baseline for SBP, DBP, pulse rate, and body weight will be summarized for all post-Baseline time points.

The number and percentage of subjects with an on-treatment PCST value, PCST low value, and PCST high value will be summarized for SBP, DBP, pulse rate, and body weight. This summary will consider all assessments after the first dose of BRV and prior to or on the date of the last dose of BRV.

Additionally, the number and percentage of subjects with a PCST value, PCST low value, and PCST high value will be summarized for the above parameters for Study Entry, each visit

during the Evaluation Period for which vital signs or body weight were scheduled to be assessed, Last Value, EDV, and FV. Percentages will be relative to the number of subjects with a value at each time point.

PCST criteria (Section 13.3.4) are based on FDA Division of Neuropharmacologic Drug Products guidelines with some UCB-defined additions.

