13.3.3 Urinalysis

Qualitative urine parameters are generally reported by a descriptive score, which differs among laboratories. For data analysis purpose, a four-point scale is used. Five-point, six-point, or seven-point scales will be collapsed into a four-point scale first. A value is considered possibly clinically significant treatment emergent abnormal if an upward shift of at least 2 degrees from the baseline occurs under investigational treatment. To collapse the results in a five-point scale into a four-point scale, the lowest two positive results will be combined (see example below). For results reported with a scale of more than five-point, please consult your study physician for how to collapse into four-point scale.

Original Five-point Scale	Four-point Scale
Negative/None	Negative/None
Trace/Rare/Mild/A Few	Trace/1+/Rare/Mild/A Few
1+	
2+/Mod	2+/Mod
3+/Sev	3+/Sev

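### The GGT abnormality flag depends on the baseline value but is also tabulated at Baseline, so its Baseline cell is about 0% by construction and later visits step above it even with no drug effect

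*SAP*

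**What the plan says.** - **Criterion.** SAP 13.3.2 flags GGT when it is "≥ 3 times of ULN, if baseline value ≤ 3 times of ULN". No other chemistry analyte in that table has a condition on the baseline value; AST and ALT, for example, have a plain threshold of 3xULN.
- **Time points.** SAP 11.3.1 says that "the number and percentage of subjects with a PCST value, PCST low value, and PCST high value will be summarized for Baseline, Study Entry", followed by the scheduled laboratory visits, EDV, Last Value and FV.
- **Denominator.** The same section says: "Percentages for each parameter and time point will be relative to the number of subjects with a value at that time point". Subjects with a high baseline are not removed.
- **Baseline.** SAP 3.3 says: "Baseline for all study outcomes will be based on baseline from the previous studies". For laboratory tests this is generally the last result up to the randomization visit of the earlier study.
- **GGT is in the table.** Protocol 10.2.16 lists it among the planned chemistry tests ("gamma-glutamyltranspeptidase (GGT), and uric acid").
- **Urinalysis.** SAP 13.3.3 says: "A value is considered possibly clinically significant treatment emergent abnormal if an upward shift of at least 2 degrees from the baseline occurs", and adds that the shift must occur on study treatment. SAP 11.3.2 nevertheless tabulates this flag at Baseline.
- **Vital signs.** These criteria (SAP 13.3.4) also involve change from baseline for adults. Here SAP 11.4.1 starts the by-visit table later: the flags "will be summarized for the above parameters for Study Entry, each visit" and so on, with no Baseline column.

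**The concern.** The study has one arm and no control group. A reader of the by-visit PCST table will therefore use the Baseline column as the reference for every later column. For AST, ALT and bilirubin that column shows the true share of subjects beyond the limit before treatment. For GGT, in the same table, it shows about zero because of how the flag is defined.

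After Baseline, ordinary within-subject variation takes some subjects from below 3xULN to above it, and they are counted. Subjects who move the other way cannot offset them, because they were never counted at Baseline. The row can then look like a liver finding that appeared on brivaracetam when nothing has changed. Subjects who start above 3xULN cannot be counted at any visit, however far GGT rises, yet they remain in the denominator.

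**Working it through.** The plan states no GGT rate, so there is no planned figure to reproduce. The first step below needs only the SAP text. The others need assumptions.

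**1. The Baseline cell.** At Baseline the value tested is the baseline value itself. The flag then requires baseline ≥ 3xULN and baseline ≤ 3xULN, which only a value of exactly 3xULN satisfies.

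**2. Later time points with no drug effect.** Assume that log(GGT/ULN) is normal with the same distribution at every time point. Let p be the share at or above 3xULN and ρ the correlation between Baseline and a later visit. With c = z(1 − p):

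- unconditional share = p at Baseline and at every later visit;
- expected flagged share at a later visit = p − P(both values ≥ c);
- the same among subjects with baseline at or below 3xULN = [p − P(both ≥ c)] / (1 − p).

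Worked case, p = 5% and ρ = 0.9: c = 1.645 and P(both ≥ c) = 3.187%. The flagged share is 5.000 − 3.187 = 1.813%. Among eligible subjects it is 1.813 / 0.95 = 1.91%.

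SAP 2.4 gives 859 enrolled, 6 of them from N01315. SAP 3.5.1 leaves those 6 out of the Safety Analysis Set, so the set has at most 859 − 6 = 853 subjects. The counts below use 853.

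| p (assumed) | Unconditional share, any time point | SAP flag at Baseline | SAP flag at a later visit, ρ = 0.95 to 0.70 | Expected subjects of 853 |
|---|---|---|---|---|
| 1% | 1% | about 0% | 0.33% to 0.73% | 2.8 to 6.3 |
| 2% | 2% | about 0% | 0.60% to 1.37% | 5.1 to 11.7 |
| 5% | 5% | about 0% | 1.29% to 3.04% | 11.0 to 25.9 |
| 10% | 10% | about 0% | 2.21% to 5.32% | 18.8 to 45.4 |

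**3. Ties and shape over time.** A simulation of 2 million subjects used whole-number GGT values, an assumed ULN of 50 and ρ = 0.9. Ties at exactly 3xULN gave a Baseline cell of 0.04% (p = 2%), 0.09% (p = 5%) and 0.15% (p = 10%). At p = 5%, four later visits gave 1.84% to 1.85%. The pattern is one step and then a flat line.

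**4. Sensitivity to GGT level.** As an alternative, take log-normal GGT with between-subject SD 0.7 and within-subject SD 0.25 to 0.30 on the log scale. The expected flagged share at a later visit is:

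| Median GGT (assumed) | SAP flag at a later visit |
|---|---|
| 0.5xULN | 0.40% to 0.52% |
| 0.7xULN | 1.1% to 1.4% |
| 1.0xULN | 2.5% to 3.1% |
| 1.2xULN | 3.5% to 4.3% |

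**5. Denominator.** Dividing by all subjects instead of eligible subjects changes little. At p = 5% and ρ = 0.9 it gives 1.81% instead of 1.91%. At p = 10% and ρ = 0.70 it gives 5.32% instead of 5.91%.

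**The case against.** The best defence is that the row does not stand alone. SAP 11.3.1 also summarizes observed GGT at each time point and its change from Baseline. With no drug effect those tables would show no systematic shift. Subjects with baseline above 3xULN are included there and in the listings. AST, ALT and bilirubin have limits with no baseline condition and would support or contradict a GGT step. All of this stands, and it limits the harm. It does not correct the PCST row.

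A second defence is that the criteria are an established set: "PCST criteria (Sections 13.3.1 and 13.3.2) are based on FDA Division of Neuropharmacologic Drug Products guidelines with some UCB-defined additions". Conditioning on baseline is also a recognisable way to define a treatment-emergent flag. That may justify the GGT rule. It does not justify applying the rule at Baseline, beside analytes whose Baseline column shows true prevalence.

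Several stronger readings are tempting, and the documents do not support them:

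- **A defect in the primary safety analysis.** SAP 2.2.1.1 limits the primary variables to TEAEs, withdrawals due to AE and SAEs. Laboratory tests come under other safety variables (SAP 2.2.1.2).
- **A rise at every visit, or one that grows.** The step appears at the first later time point and then stays flat in expectation. That point is Study Entry, which for most subjects is the last visit of the previous study (SAP 3.2.3), before the first N01125 dose. A small late visit may show no flagged subject: with p = 2% and ρ = 0.9 the probability is 0.43 with 100 subjects, against 0.0007 with 853.
- **The overall on-treatment PCST count misleads in the same way.** That summary has no Baseline column, so the false comparison does not arise there.
- **Worsening in subjects who start high is lost.** It is lost only from the PCST counts.

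For urinalysis, the criterion is expressly on-treatment and Baseline categories are tabulated separately, so that column is an untidiness more than a source of error.

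**Conclusion.** The point holds as a defect in one row of a descriptive table on an other safety variable. That the GGT Baseline cell is about 0%, apart from ties, follows from SAP 13.3.2 and 11.3.1 read together, and nothing in the SAP exempts GGT. SAP 11.4.1 already avoids the problem for vital signs.

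The size of the spurious step depends on assumptions, because the documents give no GGT distribution. It is about 0.3% to 5% per later visit (roughly 3 to 45 of at most 853 subjects) if 1% to 10% of subjects are truly at or above 3xULN and the correlation with Baseline is 0.70 to 0.95. If typical GGT is well below the upper limit of normal, the step is at the low end. The denominator effect is small throughout. No test or error rate is affected, since the SAP plans no hypothesis testing.

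**What to change.** 1. For GGT, report the unconditional share at or above 3xULN at Baseline and at each later time point, so that before and after can be compared as for AST and ALT.
2. Report the baseline-conditional GGT flag only at post-Baseline time points, as SAP 11.4.1 does for vital signs, with the denominator limited to subjects whose baseline is at or below 3xULN.
3. In SAP 11.3.2, drop the Baseline PCST column for the qualitative urinalysis parameters. The Baseline response categories in the same section already carry that information.

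The cost is a few lines of SAP wording and small changes to table shells, with no new data. The one downside is that GGT gets a slightly different layout from the other analytes, which a footnote can explain.

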13.3.3 Urinalysis

Qualitative urine parameters are generally reported by a descriptive score, which differs among laboratories. For data analysis purpose, a four-point scale is used. Five-point, six-point, or seven-point scales will be collapsed into a four-point scale first. A value is considered possibly clinically significant treatment emergent abnormal if an upward shift of at least 2 degrees from the baseline occurs under investigational treatment. To collapse the results in a five-point scale into a four-point scale, the lowest two positive results will be combined (see example below). For results reported with a scale of more than five-point, please consult your study physician for how to collapse into four-point scale.

Original Five-point Scale	Four-point Scale
Negative/None	Negative/None
Trace/Rare/Mild/A Few	Trace/1+/Rare/Mild/A Few
1+	
2+/Mod	2+/Mod
3+/Sev	3+/Sev

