11.3.2 Macroscopic urinalysis

Quantitative urinalysis parameters will be summarized in the same manner as hematology and blood chemistry parameters. Response categories are negative, 1+, 2+, and 3+ for the qualitative urinalysis parameters occult blood, leukocytes, glucose, protein, and ketones and negative and positive for nitrates. Outcome values for these parameters are mapped to the levels Negative, 1+, 2+, and 3+ as follows for purposes of summary tables and the determination of PCST:

Category	Definition
Negative	“Negative”, “NEGATIVE”, or other outcomes that clearly reflect a negative finding
1+	“1+”, “+”, “Trace”, “TRACE”, or other outcomes that clearly reflect trace amount
2+	“2+” or “++”
3+	“3+”, “+++”, or other outcomes that clearly reflect the data above 3+ (eg, “4+”, “5+” etc) or more than 4 plus signs (eg, “++++”, “+++++”etc)

For qualitative urinalysis parameters (occult blood, leukocytes, glucose, protein, ketones, and nitrates), the number and percentage of subjects with each response category will be summarized for Baseline, Study Entry, each scheduled visit during the Evaluation Period for

which urinalysis parameters were scheduled to be assessed, Last Value, EDV, and FV. Percentages for each parameter will be relative to the number of subjects with a result at each time point.

For occult blood, leukocytes, glucose, protein, ketones, and nitrates, the number and percentage of subjects with an on-treatment PCST value, PCST low value, and PCST high value will be summarized. This summary will consider all assessments after the first dose of BRV and prior to or on the date of the last dose of BRV.

Additionally, for occult blood, leukocytes, glucose, protein, ketones, and nitrates, the number and percentage of subjects with a PCST value, PCST low value, and PCST high value will be summarized for Baseline, Study Entry, each visit during the Evaluation Period for which laboratory parameters were scheduled to be assessed, EDV, Last Value, and FV. Percentages for each parameter and time point will be relative to the number of subjects with a value at that time point.

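### The nitrite PCST count is fixed at zero on its two stated levels, and is otherwise undefined because the mapping never places Positive

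*SAP*

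**What the plan says.** SAP 11.3.2 sets the scales for the qualitative urinalysis results. Five parameters have four levels: "Response categories are negative, 1+, 2+, and 3+ for the qualitative urinalysis parameters occult blood, leukocytes, glucose, protein, and ketones". The sixth has two: "negative and positive for nitrates". Protocol 10.2.16 and SAP 11.3.3 call this analyte nitrite.

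The next sentence of 11.3.2 says "Outcome values for these parameters are mapped to the levels Negative, 1+, 2+, and 3" (the last level being 3+), and gives both the summary tables and the PCST determination as its purpose. In the mapping table that follows, the 1+ row takes a single plus sign, trace, "or other outcomes that clearly reflect trace amount". No row mentions Positive.

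The section then requests PCST results for all six parameters by name: "For occult blood, leukocytes, glucose, protein, ketones, and nitrates, the number and percentage of subjects with an on-treatment PCST value, PCST low value". It asks for a count of high values as well. The same three counts are planned by visit. Separately, it plans the number and percentage of subjects in each response category, nitrates included, at Baseline, Study Entry, each scheduled Evaluation Period visit with urinalysis, Last Value, EDV and FV.

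SAP 13.3.3 holds the only urinalysis PCST criterion, an "upward shift of at least 2 degrees from the baseline" under treatment. It states "For data analysis purpose, a four-point scale is used" and explains how to shorten scales of more than four points. It does not say how to place a two-point result on four points, has no separate nitrite rule, and has no downward criterion.

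**The concern.** A criterion that asks for two steps cannot be met on a scale with only one step. If nitrite is scored on the two levels that 11.3.2 lists, its PCST row will show zero subjects because of the rule, regardless of how many turn positive. If it is scored on the four-level scale, the answer depends on a coding decision that the SAP does not record, and two programmers could produce different tables from the same data.

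Long-term safety is the primary objective (Protocol 6.1), urinalysis is a named safety variable (SAP 2.2.1.2), and Protocol 13.1.3 commits to summarizing possibly clinically significant laboratory abnormalities. A 0% in that summary should be an observation. Here it would be an artefact of the definition.

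**Working it through.** The documents give no figure to reproduce. The check is to list every baseline/on-treatment pair on each scale and count those that meet the criterion.

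**Inputs**
- Criterion (SAP 13.3.3): on-treatment level minus baseline level ≥ 2.
- Five four-level parameters (SAP 11.3.2): Negative = 0, 1+ = 1, 2+ = 2, 3+ = 3.
- Nitrite (SAP 11.3.2): negative = 0, positive = 1. As a sensitivity check, Positive is also placed at 1+, 2+ and 3+ on the four-level scale.
- Subjects (SAP 2.4 and 3.5.1): 859 enrolled, of whom 6 came from N01315 and are outside the Safety Analysis Set, so at most 859 − 6 = 853.

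**Pairs that qualify**

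| Scale | Possible pairs | Largest upward shift | Pairs with shift ≥ 2 |
|---|---|---|---|
| Four levels | 4 × 4 = 16 | 3 − 0 = 3 | 3 (Negative to 2+, Negative to 3+, 1+ to 3+) |
| Nitrite, two stated levels | 2 × 2 = 4 | 1 − 0 = 1 | 0 |
| Nitrite, Positive placed at 1+ | 4 | 1 | 0 |
| Nitrite, Positive placed at 2+ | 4 | 2 | 1 (Negative to Positive) |
| Nitrite, Positive placed at 3+ | 4 | 3 | 1 (Negative to Positive) |

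The criterion works for the five four-level parameters. For nitrite it yields nothing on the stated levels or at 1+. It works only under a placement at 2+ or 3+ that the SAP does not state.

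**What a negative-to-positive rule would count.** The documents give no nitrite rates, so the following are assumptions: 0% to 10% positive at Baseline, and 1% to 20% of the baseline-negative subjects turning positive on treatment. Expected count = 853 × (1 − baseline positivity) × conversion.
- Low end: 853 × (1 − 0.10) × 0.01 = 7.7, about 8 subjects.
- High end: 853 × (1 − 0) × 0.20 = 170.6, about 171 subjects.
- On the two stated levels, under the current rule: 0 in every case.

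**Low rows.** The criterion counts upward shifts only, so no pair on any of the six parameters can be a PCST low value. On the four-level scale there are three pairs with a downward shift of two or more, and they meet no criterion. PCST and PCST high must therefore be identical.

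**The case against.** The best reply is that PCST need not be scored on two levels at all. The mapping sentence in 11.3.2 follows a list that includes nitrates and is said to serve the PCST determination, and 13.3.3 says four points are used for analysis. On that reading nitrite goes onto the four-level scale, and coding Positive as 2+ or 3+ would make the criterion attainable. This stands in part. A reader might infer that the nitrite PCST count must be zero whatever the data show and however the table is programmed. The documents do not support that, because they leave the placement of Positive open. The reply does not rescue the plan, however: no text supports 2+ or 3+, and the nearest written entry, a single plus sign, leads to 1+ and back to zero.

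A second reply concerns consequence. A reader might infer that an artefactual 0% could not be told apart from a true absence of nitrite abnormalities. That is not so. The response-category table is required for nitrates at every scheduled time point, and SAP 3.1 provides listings of source data. A 0% PCST rate beside a non-zero Positive count would reveal the artefact. The by-visit table gives proportions at each visit, however, and does not count subjects who were negative at Baseline and turned positive. That count would have to be pieced together from the listings.

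Third, the impact is small. Leukocytes keep a four-level scale, a trace or positive result for protein, blood or leukocytes leads to microscopy (Protocol 10.2.16), and an abnormal laboratory finding can be reported as an adverse event (Protocol 12.3.1). All of this stands. The empty PCST low rows are likewise only a matter of table tidiness: they conceal no abnormality that the SAP defines, and should not be read as a second safety gap.

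**Conclusion.** The point holds in limited form. As 11.3.2 and 13.3.3 are written, the nitrite PCST count is fixed at zero on the two stated levels (largest possible shift 1, required 2). On the four-level scale it is undefined, with the nearest written mapping also giving zero. Either way, a reported 0% would say nothing about the data.

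What is lost is one within-subject summary for one dipstick analyte, the number of subjects going from negative to positive. The positive results themselves are still tabulated and listed. The analyses are descriptive and the primary safety variables are untouched, so this is a minor correction that is worth making because it is so cheap.

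The conclusion rests on the SAP text alone and assumes that no separate programming specification places Positive at 2+ or 3+. The range of about 8 to 171 subjects is illustrative and depends entirely on the assumed rates.

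**What to change.** In SAP 13.3.3, do one of the following:
- add a sentence defining nitrite PCST as Negative at Baseline to Positive on treatment; or
- remove nitrite from the PCST tables in 11.3.2 and keep its response-category table.

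If the first option is taken, exempt nitrite from the four-level mapping in 11.3.2, so that the two sections agree.

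While editing, drop the PCST low rows for the six qualitative parameters or mark them not applicable, and use one name for the analyte (nitrites in Protocol 10.2.16, nitrates in SAP 11.3.2, nitrite in SAP 11.3.3).

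The cost is a sentence or two in the SAP and a trivial program change. No new data are needed and no other analysis is affected.
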